8.2. Statistical Analysis Methods

8.2.1. General Considerations for Efficacy Analysis

Unless otherwise specified, the analyses of the treatment effect on PFS, OS and myeloprotection endpoints will be based on the FAS population. Tumor response analyses including ORR, CBR and DOR will be based on the RE population.

8.2.2. Analysis for Progression Free Survival (PFS) and Overall Survival

For PFS, the number and percentage of patients with a PFS event (radiographic disease progression or died due to any cause) or censored will be summarized along with the reasons for censoring. Furthermore, the number and percentage of patients with disease progression or who died due to any cause will be summarized with the number of PFS events as the denominator for percentage calculation. For OS, the number and percentage of patients who died or are censored will be summarized. In addition, duration of total follow-up will also be summarized.

Kaplan-Meier plots will be generated and the median, 25% and 75% percentile of PFS and OS will be estimated using the Kaplan-Meier method with their corresponding 95% confidence interval calculated based on the method by Brookmeyer and Crowley (1982). Additionally, Kaplan-Meier estimates will be provided for the survival probability along with their 95% confidence intervals (Kalbfleisch, 1980) at selected landmarks of 12, 18, and 24 months for PFS and OS.

Data listings will be generated for PFS and OS, respectively. Tumor scan data will be included in the PFS data listing, while the duration of total follow-up will be included in the OS data listing. For each listing, detailed information supporting the calculation of PFS (or OS) along with the censoring indicator, and reasons for censoring will also be included.

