# Statistical analysis methods for primary and secondary endpoints

Analysis for primary efficacy endpoint

The primary endpoint, PFS, is defined as the time (months) from the date of first dose of study drug until the date of documented radiographic disease progression (PD) per RECIST v1.1 or death due to any cause, whichever comes first. For patients who do not experience PD or are alive at the time of performing the analysis, PFS will be calculated per censoring rules detailed in the Statistical Analysis Plan. The primary analysis for PFS will be conducted at the time when 36 patients have radiographically-determined disease progression or have died. A Kaplan-Meier plot will be produced. The median, 25th percentile, and 75th percentile of PFS will be estimated using the Kaplan-Meier method with their corresponding 95% confidence internal (CI) calculated based on the method by Brookmeyer and Crowley (1982). PFS will be analyzed on the FAS population.

Analysis for secondary anti-tumor efficacy endpoints:

Tumor response:

Objective response rate is defined as the proportion of patients with best overall response (BOR) of either confirmed complete response (CR) or confirmed partial response (PR) per RECIST v1.1. ORR, along with its 95% two-sided CI using the Clopper-Pearson method, will be computed. ORR will be analyzed on the RE population.

CBR is defined as the proportion of patients with a BOR of confirmed CR, confirmed PR, or stable disease lasting 24 weeks or longer from the first date of study drug administration. CBR will be analyzed similarly as ORR based on the RE population.

DOR is the time (months) between the date of achieving first objective response (CR or PR), confirmed at the next tumor scan, and the date of documented disease progression per RECIST v1.1 or death, whichever comes first. Patients who do not experience objective CR or PR will not be included in the analysis. For patients with objective response who do not reach radiographically determined PD or die at the time of analysis, censored time will be calculated following the rules detailed in Section 12.4.6.2. The median, 25th percentile and 75th percentile will be estimated using the Kaplan-Meier method with their corresponding 95% CI calculated based on the method by Brookmeyer and Crowley (1982).

OS:

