# 12.1. Sample Size Determination

The sample size is calculated to support the primary objective of the study, that is, to evaluate trilaciclib's effect on PFS when administered prior to sacituzumab govitecan-hziy in patients with locally advanced or metastatic TNBC who received at least 2 prior treatments with at least 1 in the metastatic setting.

This single-arm study plans to enroll 45 patients during the 10-month accrual period with an approximate 30-month total study duration. With 45 patients and 14 months of follow-up after the last patient is dosed, Table 12 presents the required number of PFS events and statistical powers to detect HRs of 0.7 and 0. 8 at a 2-sided significance of 0.2 for a median PFS of the historical control group of 5.6 months, which was defined for patients without brain metastases treated with sacituzumab govitecan-hziy in the Phase 3 ASCENT trial (Bardia, 2021). The calculation is based on one-sample log-rank test (Wu, 2015) with the assumption that the survival time distributions for both study treatment and historic control group follow the Weibull distribution with a shape parameter of 1.00 (i.e., exponential distribution).

**Table 12:** Statistical Power

Hazard Ratio	Median PFS for trilaciclib + sacituzumab govitecan-hziy (Months)	•	Statistical Power
0.70	8.0	36	80%
0.80	7.0	38	54%

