#### 12.4.6. Efficacy Analyses

#### 12.4.6.1. Analyses of Primary Efficacy Endpoint – Progression-Free Survival

The primary efficacy endpoint of PFS during the study is defined as the time (months) from the date of first dose of study drug to the date of documented radiographic disease progression per RECIST v1.1 or death due to any cause, whichever comes first. PFS will be determined using all data until the last evaluable visit prior to or on the date of (i) radiographic disease progression per RECIST v1.1; (ii) withdrawal of consent to obtain additional scans on study; or (iii) initiation of subsequent anticancer therapy, whichever is earlier. Death (in absence of progressive disease [PD]) is always categorized as an event in the PFS analysis. Censoring rules for patients who do not experience PD or death at the data cutoff date will be described in the study SAP.

The primary analysis for PFS will be conducted at the time when 36 patients have radiographically-determined disease progression or have died. A Kaplan-Meier plot will be produced. The median, 25%, and 75% percentile of PFS will be estimated using the Kaplan-Meier method with their corresponding 95% CI calculated using the method by Brookmeyer and Crowley (1982).

Analysis of PFS during the study will be based on the FAS.

G1T28-213

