1.3. Sample Size Consideration

The initial sample size was calculated to support the primary objective of the study, that is, to evaluate trilaciclib's effect on PFS when administered prior to sacituzumab govitecan-hziy in patients with locally advanced or metastatic TNBC who received at least 2 prior treatments with at least 1 in the metastatic setting.

This single-arm study was initially planned to enroll 45 patients during the 10-month accrual period with an approximate 30-month total study duration. With 45 patients and 14 months of follow-up after the last patient is dosed, Table 2 presents the required number of PFS events and statistical powers to detect hazard ratios (HRs) of 0.7 and 0. 8 at a 2-sided significance of 0.2 for a median PFS of the historical control group of 5.6 months, which was defined for patients without brain metastases treated with sacituzumab govitecan-hziy in the Phase 3 ASCENT trial (Bardia, 2021). The calculation is based on a one-sample log-rank test (Wu, 2015) with the

assumption that the survival time distributions for both study treatment and historic control group follow the Weibull distribution with a shape parameter of 1.00 (i.e., exponential distribution). PASS 2019, v19.0.8 was used for the power and sample size calculation.

Table 2Statistical Power

Hazard Ratio	Median PFS for trilaciclib + sacituzumab govitecan-hziy (Months)	Expected number of events in the study	Statistical Power
0.70	8.0	36	80%
0.80	7.0	38	54%

On February 14, 2023, the sponsor decided to close enrollment to this study in order to reallocate resources to other ongoing trilaciclib clinical trials. The final sample size is 30.

G1 Therapeutics

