8. EFFICACY ANALYSIS

All efficacy analyses will be performed for the FAS population, unless specified otherwise.

The primary efficacy endpoint for this study is the treatment effects on PFS. PFS and other efficacy endpoints related to tumor response (ORR, CBR, and DOR) and myeloprotection efficacy will also be evaluated based on data collected during the treatment period (see Section 2.1).

The treatment effect on OS will be evaluated when the number of events specified in Section 2.1 are observed for OS. The clinical database will be locked for this analysis. At the time of the final planned analysis, all other efficacy analyses outlined for the study will also be conducted.

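### The stated PFS power belongs to a one-sample log-rank test that no PFS analysis section plans, and neither power nor precision is given for the final 30 patients

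*SAP*

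**What the plan says.** Both documents size the study to "evaluate trilaciclib's effect on PFS when administered prior to sacituzumab govitecan-hziy" (SAP 1.3; the Protocol Synopsis and 12.1 give the same aim). Protocol 12.1 states: "The calculation is based on one-sample log-rank test". SAP 1.3 repeats it: "The calculation is based on a one-sample log-rank test". The reference is a median PFS of 5.6 months, from sacituzumab govitecan-hziy patients without brain metastases in the Phase 3 ASCENT trial. The level is two-sided 0.2 and both distributions are exponential. With 45 patients accrued over 10 months and 14 further months of follow-up, the tables give 36 events and 80% power at a hazard ratio of 0.70, and 38 events and 54% at 0.80.

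The analysis text differs. Protocol 12.4.6.1 uses 36 events as the trigger for the primary PFS analysis and then says: "A Kaplan-Meier plot will be produced". Kaplan-Meier quartiles with Brookmeyer-Crowley 95% intervals follow. The Synopsis plans the same and adds: "PFS will be analyzed on the FAS population".

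SAP section 8 says: "The primary efficacy endpoint for this study is the treatment effects on PFS". Section 8.2.1 also speaks of a treatment effect on PFS. Section 8.2.2 then gives event and censoring counts, a plot, the statement that "the median, 25% and 75% percentile of PFS and OS will be estimated using the Kaplan-Meier method with their corresponding 95% confidence interval", and Kaplan-Meier probabilities at 12, 18 and 24 months.

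SAP 1.3 also records the early close of enrolment: "The final sample size is 30". SAP 2.1 sets a single analysis at 21 deaths, and section 10 notes that the PFS analysis was merged into it.

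**The concern.** Power is a property of a particular test. Here the test appears only in the sizing text. No PFS analysis section names a log-rank test, a reference of 5.6 months, an observed-to-expected ratio, an 80% interval or a decision rule.

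This matters because every patient receives both drugs. A Kaplan-Meier median describes the combination. Only a comparison with an outside reference says anything about what trilaciclib adds, and even that says it weakly. The plan chooses a reference and then does not use it. A reader of the report could attach the 80% to a confidence interval that it does not describe, or could set the median beside 5.6 months, or another figure, with no stated method or error rate. The early close adds a second gap: nothing says what 30 patients can show about PFS.

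**Working it through.** **Inputs** (SAP 1.3, Protocol 12.1): reference median 5.6 months; hazard ratios 0.70 and 0.80; two-sided 0.2, so z = 1.2816; uniform accrual A = 10 months; further follow-up F = 14 months; exponential PFS. No dropout is stated, so none is assumed.

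**Formulas.** λ0 = ln 2/5.6 = 0.1238 per month and λ1 = HR × λ0. The event probability is p = 1 − [exp(−λ1·F) − exp(−λ1·(A+F))]/(λ1·A). The expected reference cumulative hazard per patient is v = p/HR, and ω = v − p. Power = Φ[(√n·ω − z·σ0)/σ1], where σ0 = √v and σ1 is the standard deviation, under the alternative, of a patient's reference cumulative hazard minus the event indicator (by numerical integration).

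**Step 1: the plan's own figures, n = 45.**

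- HR 0.70: λ1 = 0.0866 and p = 1 − (0.2973 − 0.1250)/0.866 = 0.801, so events = 45 × 0.801 = 36.05. Then v = 1.1445, ω = 0.3433, σ0 = 1.0698, σ1 = 1.1307, and power = Φ[(6.708 × 0.3433 − 1.2816 × 1.0698)/1.1307] = Φ(0.824) = 79.5%. Stated: 36 and 80%.
- HR 0.80: p = 0.8413, so events = 37.9. Then ω = 0.2103, σ0 = 1.0255, σ1 = 1.0697, and power = Φ(0.090) = 53.6%. Stated: 38 and 54%.

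Both rows reproduce. With the alternative null variance (O+E)/2, power is 82.1% and 56.1%. Simulation (200,000 trials per setting) gives 81-83% and 53-55% across the two variances.

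**Step 2: the same test at n = 30.** On the original schedule, HR 0.70 gives 30 × 0.801 = 24.0 events and Φ[(5.477 × 0.3433 − 1.3710)/1.1307] = Φ(0.451) = 67% (71% with the other variance). HR 0.80 gives 25.2 events and 44% (46%).

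That schedule is only one scenario. The Synopsis expected the first patient in Q4 2021 and enrolment closed on 14 February 2023, which suggests about 14 to 16 months of accrual. Assuming 15 months, at HR 0.70:

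| Further follow-up (assumed) | Events | Power, variance E to (O+E)/2 |
|---|---|---|
| 8 months | 21.6 | 65-68% |
| 14 months | 25.0 | 68-72% |
| 20 months | 27.0 | 70-73% |

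The range is therefore about 22 to 27 events and 65-73%. Thirty-six events are impossible in 30 patients.

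**Step 3: what the planned analysis gives at n = 30** (20,000 simulated trials per setting, original schedule, medians of the Brookmeyer-Crowley limits).

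- True median 8.0 months: 95% interval about 4.4 to 13.2, width 8.5.
- True median 5.6 months: 95% interval about 3.1 to 9.2, width 6.0.

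At a true median of 8.0, the 95% interval lies wholly above 5.6 in about 22% of trials. An 80% interval does so in about 50%. The planned interval does not inherit the power of the test, and only part of the gap is the confidence level.

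**Step 4: what a supportive comparison would look like.** With O = 24 and O/E = 0.70, E = 34.3. Exact Poisson limits for O are 17.97 to 31.58 (80%) and 15.38 to 35.71 (95%). Dividing by 34.3 gives 0.52-0.92 and 0.45-1.04.

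**The case against.** The strongest defence is that the documents claim little. Protocol 6.1 calls the study exploratory. There is no success rule. SAP 1.3 labels the sizing as initial and does not claim 80% power for 30 patients. The output is an abbreviated report. A reader can also set the median and its interval beside 5.6 months, which stands in the same SAP. All of this is fair, and it limits the point to what the PFS result can be said to show. It does not give the power figures an analysis to belong to.

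A reader might infer that the SAP silently dropped a specified test and that section 10 should have recorded it. The documents do not support that. The protocol's own PFS analysis text never contained the test. The mismatch starts inside the protocol, between 12.1 and 12.4.6.1, and the SAP carries it forward. A reader might also infer that the power figures are wrong. They are not: they reproduce for the test at 45 patients.

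There is a real case against adding the test. The nominal one-sided error is 10%. In simulation at 30 patients with no effect, it becomes 23-25% if the true control median is 6.3 months, the upper confidence limit quoted in Protocol 4.1. It becomes 27-30% if PFS has a Weibull shape of 0.8, an assumed value with no source in the documents. The test would also be specified after enrolment closed in an open-label trial, and it cannot isolate trilaciclib's effect as a randomised control would. These objections stand. They are why the comparison is offered only as a supportive addition.

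**Conclusion.** The concern holds as a mismatch between sizing and analysis. The 80% and 54% figures are correct for a one-sample log-rank test with 45 patients, but they describe nothing that either document plans to report. The treatment effect on PFS is never set against the 5.6-month reference. For the final 30 patients no power or precision is given. The test would have about 65-73% power at a hazard ratio of 0.70, and the planned 95% interval for the median would typically span 8 to 9 months if the true median is 8.0.

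These figures rest on exponential PFS, uniform accrual, no dropout and the accrual and follow-up times shown. Actual follow-up will depend on when the 21st death occurs. It would be too strong to say that a confirmatory conclusion is lost, because the study makes none. The point is worth fixing because correction needs no new data.

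**What to change.** **Minimum.** In SAP 1.3 and 8.2.2, state three things: the 80% and 54% figures apply to a one-sample log-rank test with 45 patients and do not describe the reported Kaplan-Meier analysis; PFS is estimation-only; and the expected precision with 30 patients is a typical 95% interval for the median of about 4.4 to 13 months if the true median is 8.0 (about 3.1 to 9.2 if it is 5.6). This costs two or three sentences.

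**Preferred addition.** Keep the Kaplan-Meier summaries and add to SAP 8.2.2 a supportive one-sample log-rank comparison of PFS in the full analysis set with an exponential reference of median 5.6 months. Report O, E and O/E with 80% and 95% intervals, and label the analysis as specified after enrolment closed. Restate power for 30 patients as a range (about 22 to 27 events, 65-73% at a hazard ratio of 0.70). Add one sensitivity row with a 6.3-month reference. List it in section 10 as an addition to the protocol's analysis; if the SAP is already signed off, SAP section 1 sends such changes to the study report. This costs one paragraph and one table.

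**Downsides to state with it.** The result depends on the benchmark and the exponential shape, with the error rates given above. The 6.3-month row is strict: if the true control median is 5.6 and there is no effect, it favours trilaciclib in 2-3% of trials, but power at a true median of 8.0 falls to 44-47%.

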8.2.3. Analysis for Secondary Endpoints - Anti-tumor Efficacy Endpoints

The analysis for BOR, CBR, and ORR (see variable definitions in Section 8.1.2) will be based on the RE population.

Tumor response status classified by BOR will be tabulated with the number and percentage of patients in each category of CR, PR, SD, PD or NE, where the percentages are calculated based on the number of patients in the RE population.

ORR along with its exact 95% two-sided CI using the Clopper-Pearson method will be computed.

Confirmed ORR and CBR will be summarized and analyzed using the same methods as are used for the ORR.

For patients who achieved CR or PR as BOR status, DOR will be analyzed. The Kaplan-Meier method will be used to estimate the median, 25% and 75% percentile of DOR, along with its 95% CI calculated using the method by Brookmeyer and Crowley (1982).

Data listings will include tumor scan data, Investigator determined timepoint responses and BOR, and programmatically derived tumor response status, and confirmed tumor response status.

G1 Therapeutics

8.2.4. Analysis for Secondary Endpoints - Myeloprotection Endpoints

Statistical analysis methods for myelosuppression endpoints derived based on data collected during the treatment are described in this section. No corresponding data listings will be provided.

8.2.4.1. Analysis for Binary Myelosuppression Endpoints

For each binary myelosuppression endpoint as specified in Table 7 (Section 8.1.4), the number and percentage of patients with at least one occurrence during the treatment period will be summarized.

8.2.4.2. Analysis for Counting Myelosuppression Endpoints

For the counting myelosuppression endpoints as specified in Table 7 (Section 8.1.4), the total number of the events, and raw event rate per 100 units (weeks or cycles) will be summarized.

8.3. Handling of Missing Data

In general, the observed data will be used for analyses or data summary. That is, no missing data imputation will be performed.

Missing data impact on time-to-event endpoints, including primary endpoint PFS, is in general managed by derivation rules (Section 8.1).

G1 Therapeutics

9. SAFETY ANALYSIS

9.1. General Consideration of Safety Analysis

Safety data summaries will be based on the safety population as defined in Section 3.3 of this SAP.

Safety data collected during treatment will be summarized at the final analysis.

Safety and tolerability will be assessed by AEs, laboratory tests, vital signs and ECG. Safety data will be summarized using descriptive statistics for all patients when appropriate. All safety data collected through scheduled and non-scheduled visits during the treatment period will be included in the safety data analyses. The treatment period for a patient is defined as the time interval from date of C1D1 to the date of End of Treatment (EOT) visit. If the EOT visit does not occur for the patient, then 14 days post the last dose in the last cycle will be used as the end date of treatment. Missing safety data will generally not be imputed, unless otherwise specified.

Baseline assessment is, in general, defined as the last non-missing observation prior to receiving the first dose of any study drug.

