# 11.3.6.1. Time Period and Frequency for Collecting Adverse and Serious Adverse Event Information

AEs will be collected starting from the first dose of study drug through the Safety Follow-up Visit. Any SAE occurring between the date the patient signs informed consent and the first dose of any study drug, and which the Investigator feels is related to a study specific procedure (i.e., would not have occurred unless the patient was on the study), should also be reported. Any AEs that occur between the date of signing informed consent and the first dose of study drug should be recorded as Medical History.

All SAEs will be recorded and reported to G1 Therapeutics pharmacovigilance (PVG) or designee immediately and should not exceed 24 hours after becoming aware of the event, as indicated in Section 17.2.

G1T28-213

Investigators are not obligated to actively seek AE or SAE information after 30 days following the last dose of study drugs on this study. However, if the Investigator learns of any SAE, including a death, at any time after a patient has been discharged from the study, and he/she considers the event to be reasonably related to the study intervention or study participation, the Investigator or designee must promptly notify G1 Therapeutics PVG or designee.

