#### 11.5. End of Treatment Visit

When a patient permanently discontinues study treatment, the patient should complete an End of Treatment Visit 14 days (±7 days) from last dose of study drug as outlined in Table 6.

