## 11.6. Safety Follow-up Visit

The patient should complete a Safety Follow-up Visit 30 days (+7 days) from last dose of study drug as outlined in Table 6. This visit may occur at the study site, or can be via telephone, email, or by receiving information from a family member or healthcare provider.

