9.2. Adverse Events

9.2.1. Definition and Classification of Adverse Events

AEs are defined as those AEs occurring on or worsening in severity after the first dose of any study drug (i.e., the conventional treatment-emergent AEs). Only AEs as described above are collected in the study database. All AEs are reported since the first dose of any study drug until end of safety follow-up (30 days after the last dose of study drug). SAEs thought to be related to a study specific procedure are also collected between the time the patient signs the informed consent and the first dose of any study drug.

AEs will be coded from verbatim text to PT and grouped by primary SOC according to MedDRA version 26.1 or later. The severity (toxicity grades 1-5) of AEs will be graded according to the NCI CTCAE version 5.0 by the Investigator.

Hematologic Adverse Events

AEs related to hematologic toxicity will be collapsed based on the PTs from MedDRA version 26.1 or later and will be summarized separately (see Section 9.2.3). Table 8 outlines those PTs that will be collapsed.

Term presented in the Output	Preferred Term
Neutropenia	Neutropenia
	Neutrophil count decreased
Anemia	Anemia
	Anaemia
	Red blood cell count decreased

Table 8	Hematologic Preferred Terms to be Collapsed
---------	---

Term presented in the Output	Preferred Term		
	Hemoglobin decreased		
Thrombocytopenia	Thrombocytopenia		
	Platelet count decreased		
Lymphocytopenia	Lymphocytopenia		
	Lymphopenia		
	Lymphocyte count decreased		
Leukopenia	Leukopenia		
	White blood cell count decreased		

Trilaciclib Adverse Events of Special Interest

AEs of special interest (AESI) for trilaciclib have been identified, reflecting either the findings in the AEs from the previous studies of trilaciclib or class effects for CDK 4/6 inhibitors. AESI for trilaciclib will be identified by searching MedDRA PTs based on the Customized MedDRA Queries as detailed in Appendix 2.

Specifically, trilaciclib AESI include the following 5 categories:

- Injection site reaction/Phlebitis/Thrombophlebitis
- Acute drug hypersensitivity reaction
- Hepatotoxicity
- Interstitial lung disease /Pneumonitis
- Embolic and thrombotic events, venous

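### SAP 9.1 ends the safety analysis window at the End of Treatment visit, although AEs are collected and reported to about day 30: the AE tables need an explicit window

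*SAP*

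**What the plan says.** SAP 9.1 lists AEs, laboratory tests, vital signs and ECG as the safety data. It then gives an inclusion rule: "All safety data collected through scheduled and non-scheduled visits during the treatment period will be included in the safety data analyses". It closes the period as follows: "The treatment period for a patient is defined as the time interval from date of C1D1 to the date of End of Treatment" visit. The fallback is: "If the EOT visit does not occur for the patient, then 14 days post the last dose in the last cycle will be used".

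The AE provisions run longer. SAP 9.2.1 says: "All AEs are reported since the first dose of any study drug until end of safety follow-up", which it puts at 30 days after the last dose. Protocol 11.3.6.1 agrees: "AEs will be collected starting from the first dose of study drug through the Safety Follow-up Visit". SAP 9.2.3, which specifies the AE tables, states no time limit.

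The visit timings are in Protocol 11.5 ("End of Treatment Visit 14 days (±7 days) from last dose of study drug") and Protocol 11.6 ("Safety Follow-up Visit 30 days (+7 days) from last dose of study drug").

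Protocol 12.4.7 includes data from all scheduled and unscheduled visits in the safety analyses and does not mention a treatment period.

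SAP 9.2.2 sets a completely missing AE stop date, for an AE not ongoing at data cutoff, to the End of Treatment (EOT) visit date, or to last dose plus 14 days if that visit did not take place.

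**The concern.** Safety and tolerability is a stated secondary objective, and the AE tables are its main output. Two people programming from the same SAP could produce different tables. One would restrict AEs to the treatment period as 9.1 defines it. The other would take all AEs as 9.2.1 defines them.

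The restricted version would leave out AEs that sites were asked to collect and that start between the EOT visit and the Safety Follow-up. Removing events cannot raise a count, so any error goes in the favourable direction. The protocol does not break the tie, because SAP section 1 gives the SAP precedence where the two documents differ.

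**Working it through.** The plan states no figure to reproduce. The check compares the texts and then does the window arithmetic.

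**Where each provision ends the window for AEs**

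| Provision | End of window |
|---|---|
| SAP 9.1, inclusion rule | EOT visit, or last dose + 14 days |
| SAP 9.2.1, AE definition and reporting | 30 days after last dose |
| SAP 9.2.3, AE tables | none stated |
| Protocol 11.3.6.1, AE collection | Safety Follow-up Visit |
| Protocol 12.4.7, safety analyses | none stated |

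The 9.1 sentence closely follows the one in Protocol 12.4.7 but adds the treatment-period condition. SAP section 10, which lists changes from the protocol, does not mention a narrower safety window. The protocol's study phases do not help either: the synopsis ends the Treatment Phase at the Safety Follow-up Visit, whereas Protocol 6.1 (repeated in SAP 1.1) ends it at the EOT visit.

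**Length of the uncovered interval**

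I assume that a filter based on 9.1 would act on AE onset date. Days are counted from the last dose.

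Gap = end of AE window − day of EOT visit.

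- Nominal: 30 − 14 = 16 days. This is also the gap when the last-dose-plus-14 fallback applies.
- Latest EOT visit (14 + 7 = day 21): 30 − 21 = 9 days.
- Earliest EOT visit (14 − 7 = day 7): 30 − 7 = 23 days.
- If collection runs to a Safety Follow-up visit on day 37 (30 + 7): 37 − 21 = 16 to 37 − 7 = 30 days.

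**Which outputs are exposed**

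- Exposed: the SAP 9.2.3 summaries of AEs, SAEs, trilaciclib AESIs and AEs leading to death.
- Hardly exposed: laboratory, vital sign and ECG summaries. The Schedule of Assessments places none of these after the EOT visit, so only unscheduled tests could be involved.
- Not exposed: the AE and SAE listings (SAP 4.2 and 9.2.3), and the SAP 5.1 table of all deaths during the study by primary reason, which has an adverse-event category.

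**Effect per patient**

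With 30 patients enrolled (SAP 1.1) and all of them dosed (an assumption), one patient missed from a row changes that rate by 1/30 = 3.3 percentage points.

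**Stop-date rule**

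Take an EOT visit on day 14 and an AE that starts on day 20, has resolved, and has no recorded stop date. SAP 9.2.2 sets the stop date to day 14, which is 14 − 20 = −6 days relative to onset. The start-versus-stop comparison in 9.2.2 applies only when the start date was imputed, and the later check compares the stop date with death only. Neither corrects the error.

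**The case against.** The best defence is that 9.1 is a general section that says what is included and never says that anything else is excluded. The AE-specific sections should govern AEs. They define AEs by a starting point alone, carry reporting to 30 days, and build tables with no cutoff. The absence of a narrower window from SAP section 10 suggests that none was intended. This stands to the extent that exclusion is a literal reading and not a certain result. It does not remove the conflict: 9.1 names AEs, defines the period precisely, and exempts nothing.

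A reader might infer that late AEs, SAEs and fatal AEs will disappear from the report. The documents do not support that. Only summary tables are at risk; listings and the SAP 5.1 death table would still show the events. Nor are all safety analyses affected, since the non-AE assessments stop at the EOT visit by design.

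A reader might also try to size the loss from expected deaths in the weeks after treatment. That would measure the wrong thing. The filter would act on AE onset and not on date of death, Protocol 17.2.2 keeps deaths due to progression outside the SAE definition, and any post-treatment survival figure would be an assumption. The length of the gap is not a proxy either, because AEs are not spread evenly over calendar days.

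The AESI history in Protocol 4.3.3.1 also argues for a small effect. Median onset after the preceding trilaciclib dose was 1 day for both injection-site reactions (range 1 to 15) and hypersensitivity (range 1 to 28). The single pneumonitis case came 2 months after discontinuation, outside either window. The upper ends of the two ranges do pass day 14, so late AESIs are possible but probably few.

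**Conclusion.** The point holds as an unresolved conflict inside the SAP, and between the SAP and the protocol, over the AE analysis window. On a literal application of 9.1, the AE summary tables would omit events with onset in a nominal 16-day interval, or 9 to 23 days across the EOT visit window, counted to day 30. The direction is known: counts can only fall. The number of events is not known and cannot be computed from the documents. The stop-date rule is a separate, smaller defect. It leaves patient counts in the incidence tables unchanged but can produce impossible dates.

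The conclusion assumes that a 9.1 filter would use onset date and that visits fall within their stated windows. It should be settled before the tables are programmed; it does not call the trial's safety conclusions into question.

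**What to change.** 1. In SAP 9.1 or 9.2.3, state that the AE, SAE, AESI and fatal-AE tables include every AE with onset from first dose through the end of safety follow-up. Say whether that end is day 30 or the actual visit date (up to day 37).
2. Keep the EOT-bounded period for laboratory, vital sign and ECG summaries, and say that it applies only to those.
3. Change SAP 9.2.2 so that an imputed stop date cannot precede onset, for example by using the end of safety follow-up for a completely missing stop date. Keep the existing cap at date of death.
4. If an EOT cutoff for AEs was intended after all, list it with a reason in SAP section 10.

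The cost is a few sentences of SAP text and a small programming change. No new data are needed. The only downside is that reported AE counts may rise slightly.
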